### **SIGNIFICANCE (Criterion 2, 4, RQ-1)**

This grant addresses PCORI's priority topic on TBI to "Compare the effectiveness of multidisciplinary rehabilitation programs for moderate-to-severe TBI in non-military or veteran adults." Consistent with this priority, we seek to improve the "transition between acute inpatient rehabilitation and subsequent care, and examine the impact on a patient's functional status." By leveraging our existing TBIMS infrastructure, which includes a high volume of patients with moderate-to-severe TBI, we can readily examine "pre-specified patient and clinical subgroups." Our grant is also consistent with several IOM priorities, e.g., to compare the effectiveness of comprehensive care coordination programs; diverse models of transition support services for adults with complex health care needs; different quality improvement strategies in disease prevention, acute care, chronic disease care, and rehabilitation services for diverse populations; and different strategies to engage and retain patients in care and to delineate barriers to care, especially for members of populations that experience health disparities. Our grant is also consistent with AHRQ priorities including outpatient case management for adults with medical illnesses and complex care needs, and multidisciplinary rehabilitation programs for moderate-to-severe TBI in adults.

Equally important if not more so, improving transition care is a high priority for our stakeholders. Given that our study team has been examining TBI as a chronic condition for several years, we have sought input from individuals with brain injury to understand how they interact with the healthcare system and this made us aware of the significance of getting individuals help early after TBI to connect them with resources and also with others with brain injury. We have heard from individuals with TBI and their families that even when they received excellent hospital care, the transition to the community was difficult. In addition, clinicians describe even more concern for those individuals who do not have available and invested family members to assist as they transition out of the hospital.

Our Professional Stakeholders who work for advocacy organizations describe a struggle in knowing the best approach to supporting members of the TBI community. For example, one of our Professional Stakeholders stated *“I have attended conferences to learn how we can best provide assistance to individuals with brain injury, but when I read about ‘case management’ everyone is describing something different. If you could provide evidence for a standardized approach following discharge you can improve how transitional care is given across the country. We will immediately adopt it.”*

**Evidence from this comparative effectiveness study will aid in decision making for health care systems and advocacy groups on best practices for transition and coordination of care (RQ-3, RQ-5).** Rehabilitation administrators are faced with the question of how they can provide patients with discharge care that will reduce the likelihood of readmission into the hospital while optimizing patients' ability to successfully resume community living. Currently, accredited rehabilitation units utilize a discharge care plan that meets CARF standards under the assumption that these standards maximize outcome. However, the discharge approach within the VHA and other systems suggest that more intensive and temporally distributed case management as in our Rehabilitation Transition Plan (RTP) may be a more effective model. Unfortunately, while similar models have been shown to be effective with other populations, they have not been directly compared to the current standard approach used across the country. While requiring additional personnel, the RTP could reduce hospital readmissions that incur penalties levied by the Centers for Medicare and Medicaid Services which may balance any cost differential. In preparation for the current application, researchers from the six TBIMS sites partnering for this grant conducted a series of focus groups with patients, family members, and caregivers. Our group's preliminary data suggest that, despite following current CARF standards for discharge, there are unacceptably high rates of missed follow-up clinical visits, gaps or lapses in clinical care, and overall dissatisfaction with the information, education, and resource facilitation available. Additional discussion with our Patient and Family Stakeholders highlighted the need for improved follow up including education, communication, and support during the transition from inpatient rehabilitation to the next level of care.

In addition to our Patient and Family Stakeholders, members of our study team have been leading the research agenda on conceptualizing TBI as a chronic condition which requires setting individuals on an early positive trajectory to maximize their function and quality of life and reduce secondary conditions. The annual Galveston Brain Injury Conference (GBIC) convenes a group of experts in TBI with a goal of advancing research and clinical care. In the last 5 years, experts including consumer representatives, clinicians, researchers, and policy members focused on the topic of “Brain Injury as a Chronic Condition.” GBIC leaders, including numerous members of our research team, actively participated in this initiative. Case management that supports a tailored comprehensive discharge plan was identified as an important component to improve outcomes and reduce chronic conditions. Conceptualizing TBI as a chronic condition given the vast, complex array of problems and the lack of centralized TBI care in the community makes the prevention or delay of chronic conditions through early detection and intervention an important goal.

As part of the GBIC, investigators from two study sites (WA and NY) conducted a series of focus groups to learn how individuals with brain injury seek and access health care. Groups were asked a series of open-ended questions about their experiences with health care after brain injury, including any barriers or facilitators that have affected their ability to access and manage health care. Participants were, on average, 17 years post-injury, and qualitative analysis of focus group content identified key themes.

Discharge from the hospital, whether from an acute care hospital, rehabilitation unit, or nursing facility, was frequently identified as a challenging time for the patient and family, with several participants reporting that they were given insufficient information or poorly timed information. Several focus group participants remembered having been given a packet or binder of information upon discharge from the unit, but indicated that they (or their families) were too overwhelmed to recall the information provided, and many indicated that they had never even looked at the materials. Another commonly identified theme centered on gaps in care in the community, and most of the examples given by participants occurred during the transition from IRF to the next level of care. Some participants acknowledged missing follow-up appointments and not knowing how to reschedule, others indicated they were never given follow-up appointments, and still others reported considerable lags in accessing rehabilitation therapies (such as physical therapy) because they were unsure how to find specialty providers in their communities.

**There has also been research to indicate access to care and TBI-related services are primary needs in the first years after injury.** One study site (NY) conducted a survey of individuals with TBI (or their caregiver) to evaluate satisfaction across 26 aspects of daily life and identify unmet needs that contribute to dissatisfaction. Although the interview asked about a wide range of social roles and activities, some of the most commonly identified unmet needs in the first year post-injury were in access to information and resources about TBI or disability, access to TBI-related services, and understanding the challenges related to TBI. This study was cross-sectional and did not follow participants over time, but individuals who were many years post-injury and reported similar needs for information, resources and services also reported dissatisfaction with their physical health and interpersonal relationships. These findings demonstrate that: (a) Insufficient information about TBI and inadequate access to local resources and services are common areas of unmet need and sources of dissatisfaction in the early post-acute stage after TBI, (b) failure to meet these needs early in the post-acute stage of recovery may represent a missed opportunity to help a person with TBI and his/her family establish systems of care and other resources needed for longer term medical management and maintenance of interpersonal relationships. In addition, there is evidence to suggest that assistance is needed to “negotiate the rehabilitation maze” and in tailoring education to be specific to each individual’s injury at the transition from hospital to the community.

#### **PATIENT POPULATION (PC-2, RQ-3, IR-1)**

The target population is composed of all patients with moderate-to-severe TBI age 18 and older receiving inpatient rehabilitation in the United States. The sample will be composed of consecutive neurorehabilitation admissions of patients with moderate-to-severe TBI to one of six existing NIDILRR funded TBI Model System Centers, whose data have been shown to be representative of the target population (**PC-2**). Using the data from the six TBIMS sites for 2015, the gender and racial breakdown of the proposed sample is described below in the Human Subjects Section. The sample is expected to include individuals with TBI of sufficient severity to warrant inpatient rehabilitation. Those with TBI enrolled in the TBIMS have a median age of 38 years with predominantly moderate-to-severe TBI using Emergency Room Glasgow Coma Scale (GCS) scores which are captured in TBIMS data collection (Mean GCS= 9.91) in addition to multiple other severity indicators (imaging, duration of coma, PTA).

Data from the TBI National Data Center, which is the repository of longitudinal data from all TBIMS centers, provided historical data from 2015 across the six study sites. Rehabilitation admissions, TBIMS eligibility, and consent rates show that there were 764 individuals who were discharged from inpatient rehabilitation across the six study sites.

Of those discharges, 430 were found to meet eligibility criteria for the TBIMS as described in the Research Plan inclusion/exclusion criteria, which is a very conservative estimate of our volume as we will not limit enrollment in the current study to only those admitted into the system of care within 72 hours of injury (as required for TBIMS enrollment). The enrollment rate for the six sites involved in this grant is 81% from October 2015 through October 2016. In 2015 alone, 345 individuals who had a TBI and were eligible enrolled into the TBIMS across the 6 study sites. Over 3 years of enrollment, we conservatively estimate that 900 participants will consent to enroll into the proposed study.

Due to the existing infrastructure of the TBIMS at each study site, identification of eligible TBIMS participants is already in place. Each study site follows TBIMS Standard Operating Procedures (SOP) for enrollment, consent, and tracking of reasons for non-consent. Data regarding eligibility, enrollment success, and missing data are put into site-specific reports that are reviewed at each site and at the national level to ensure that barriers to successful enrollment and follow-up are addressed. This infrastructure will be utilized for the current project to monitor ongoing study enrollment and attrition. We will also use the existing TBIMS meeting infrastructure (teleconferences and TBIMS Project Director face-to-face meetings) to address study conduct on an ongoing basis. Finally, barriers such as patient inability to consent to the study are well addressed in the existing TBIMS infrastructure. Due to the cognitive impairments common after TBI, TBIMS staff have a SOP in place for determining patient capacity to consent or to obtain proxy medical consent. Once a patient has regained the capacity to consent, they are re-consented for TBIMS purposes. This study will use the same SOP for consenting participants.

### **Data Sources and Resources (IR-1)**

Data collected as part of the national longitudinal TBIMS database during inpatient rehabilitation and at 12-months post-injury will be available for the majority of participants in the proposed study. These uniform data elements will be collected from individuals who are not enrolled in TBIMS but who enroll in the current study to ensure consistency. TBIMS data elements include demographic variables, information about pre-injury social history, detailed data on injury type and severity, and functional status at rehabilitation admission and discharge (<https://www.tbindsc.org/Syllabus.aspx>).

### **STUDY DESIGN OR APPROACH (Criterion 3)**

A 1:1 randomized controlled trial design will compare the effectiveness of two established methods of managing transition from IRF discharge to the next phase of care, stratifying by site and discharge to another facility (e.g., skilled nursing facility) vs. discharge to home/community. We are stratifying on discharge destination based on the relatively lower frequency of discharge to facility (22% across all 6 TBIMS sites in 2015). However, we chose to include discharge to facility for inclusiveness and because our stakeholders encouraged it. For example, we heard "*It would be nice to have an extra advocate*" from a focus group member whose family member was discharged to a skilled nursing facility and experienced poor follow-through of rehabilitation recommendations.

Reporting of the results will follow the CONSORT guidelines (**IR-6**). The extent to which a study design is explanatory vs. pragmatic lies along a continuum, which Tosh and Thorpe have operationalized into evaluation tools. Using the Pragmascope tool, which is an adaptation of Thorpe's PRECIS tool modified for mental health studies, **our study design is highly pragmatic** as determined by the 10-item tool.

For example, our design ensures that our study includes the entire target population and allows for noncompliance based on participant preference. Both interventions are happening in everyday practice in other settings such as in CARF-accredited IRFs and the VHA, and both allow for flexibility based on participant needs and does not require high level expertise of the TBI Care Manager to be delivered. However, our primary outcomes are chosen by our Patient and Family Stakeholders, which will require patient-report and cannot be abstracted from medical records. Our secondary outcomes include objective indicators such as healthcare utilization and unplanned hospital readmissions. We also plan to compensate participants and their caregivers for the time spent to complete our outcome assessments.

The two established methods, described below (RQ-5), are (1) a standardized version of existing discharge procedures used at all six sites and (2) a standardized telephone-delivered case management approach that extends beyond the point of discharge, based on the protocol used within the VHA and enhanced with input from our Patient and Family Stakeholders. Research assistants (RA) will be blinded to participant group assignment and will conduct outcome assessments at 3, 6, 9, and 12 months post-discharge, with primary outcome of group comparison at the end of the intervention period (6 months post-discharge). The success of the blinding will be evaluated by having the outcome data collectors complete an assessment of each participant's group assignment after completing the outcome assessments and those will be reviewed for accuracy and reported with the final outcomes. We have successfully maintained blinding of outcomes assessment in trials previously.

The **Rehabilitation Discharge Plan (RDP)** condition is the CARF standard method to prepare the patient and family for discharge from inpatient TBI rehabilitation. The RDP is already in place with few variations at the six participating TBIMS centers. This RDP approach is consistent with evidence-based approaches to discharge planning that have been supported by PCORI, AHRQ and NIH. Considerable evidence exists demonstrating that this form of discharge planning results in reduced 30-day hospital readmissions and improved follow-up with outpatient appointments, improved patient satisfaction, and decreased duration of inpatient readmission and all-cause mortality compared to a non-standardized approach.

The RDP includes elements common to all centers: specific details on follow up for ongoing medical care, safety recommendations, medication lists and instructions, common symptoms to monitor, and information on healthy behaviors such as an individual's home exercise program and diet. Recommended follow up care, such as physician visits, therapies, and/or home health care, is collected upon discharge to allow comparison between groups.

The **Rehabilitation Transition Plan (RTP)** protocol will include RDP with the addition of transitional care. RTP was chosen based on literature supporting a more intensive, temporally extended and coordinated approach for patients likely to experience significant and prolonged problems after injury, i.e., those with moderate-to-severe TBI. The RTP intervention will be delivered by a TBI Care Manager (TCM) primarily via telephone. Focus group members emphasized the need for assistance beyond providing discharge education. As described in more detail below, the RTP comparator incorporates treatment elements with known efficacy from the VHA with input from our stakeholders.

Case management, including needs assessment and resource facilitation to address unmet needs, has been an important element in several successful post-acute TBI trials. Importantly, in response to the recent influx of war casualties that included many patients with TBI and polytrauma, the VHA established Case Management Standards of Practice designed to “avoid duplication, poor timing, or missed care opportunities” using a “process that assesses, advocates, plans, implements, monitors, and evaluates health care options and services so that they meet the needs of the individual patient” (p.2). The VHA model is similar to the RTP model to be used in the proposed study, but has not been empirically tested against standard care. Resource facilitation, which is included as a key component of RTP, has been used successfully in TBI to improve community participation and return to work compared to standard care. While these strategies have been recommended by several consensus practice guidelines, implementation and provision of such interventions are not consistent, therefore research is needed to examine a well-defined approach to resource facilitation. Telephone-based interventions have been successfully used to assist in transitioning from IRF to the community following TBI. Like the RDP comparator, the RTP intervention has been standardized for the purposes of this trial, and we plan to measure individual elements provided to each patient to maximize our ability to associate care elements with primary and secondary outcomes.

### **Specific Aims and Hypotheses**

**Aim 1:** To compare the effectiveness of Standardized Discharge Care (SDC) as labeled in our original application and grant proposal, henceforth referred to as the “Rehabilitation Discharge Plan” (RDP), vs. SDC plus Optimized Transition Care (OTC) as labeled in our original application and grant proposal, henceforth referred to as “Rehabilitation Transition Plan” (RTP), RTP on improving patient-reported outcomes of (1) participation, as measured by the Participation Assessment with Recombined Tools-Objective 17 (PART-O-17) and (2) health-related quality of life, as measured by the Quality of Life after Brain Injury Scale (QoLIBRI), for individuals with moderate-to-severe TBI who are discharged from inpatient rehabilitation.

**Hypothesis 1:** Patients randomized to RTP will report better participation and health-related quality of life at the end of intervention (6-months post-discharge; **primary outcome**) and one year post-discharge compared to patients randomized to RDP.

**Aim 2:** To compare the trajectory of improvement across the first year post-discharge (with measurement at 3, 6, 9, and 12 months post-discharge) on patient-reported outcomes of (1) participation and (2) quality of life.

**Hypothesis 2:** Patients randomized to RTP will experience a steeper trajectory of improvement in participation and quality of life over 12 months compared to patients randomized to RDP.

**Aim 3:** To compare differences in healthcare utilization between RDP vs. RTP across the first year post-discharge.

**Hypothesis 3:** Patients randomized to RTP will complete a higher proportion of planned outpatient visits and have fewer urgent care visits or unplanned hospitalizations across the first year post-discharge, compared to patients randomized to RDP.

**Aim 4:** Caregiver outcomes: To compare the effectiveness of RDP vs. RTP on caregiver burden, health-related quality of life (HRQOL), satisfaction with roles and activities as measured by the Bakas Caregiving Outcomes Scale, the Zarit Burden Interview, SF-12, the PROMIS Satisfaction with Social Roles and Activities and assessment of Required Assistance and Time Spent Caregiving.

**Hypothesis 4a:** Caregivers of patients randomized to RTP will report lower caregiver burden at 6-months post-discharge, compared to caregivers of patients randomized to RDP.

**Hypothesis 4b:** Caregivers of patients randomized to RTP will report a steeper trajectory of improvement in caregiver burden over time, compared to caregivers of patients randomized to RDP.

### **Heterogeneity of Treatment Effects (HT-1, HT-2, HT-4, RQ-4)**

The interventions being compared in this study are highly patient-centered and will be tailored to each patient's individual needs. The analytic plan will compare the two approaches (Rehabilitation Discharge Plan, RDP vs. Rehabilitation Transition Plan, RTP), as opposed to compare the specific elements which will vary across all participants based on their individual needs. Consequently, we expect that some patient subgroups may be more or less likely to reap maximal benefit from the interventions under study. We will examine the effects of the intervention on patient subgroups defined by factors known or hypothesized in the literature to have associations with poorer TBI outcome and which are relevant to the implementation of the RTP in a clinical setting: discharge to facility (as opposed to community), being of minority race/ethnicity, older age, male, with lack of or low degree of caregiver involvement, high level of severity of TBI, presence of pre-injury psychosocial limitations (e.g., unemployment, substance abuse) and having medical or psychiatric comorbidity. In addition, we will explore whether there were differences according to study site, resource variability (e.g., community resources available) and insurance type.

For the subgroup analysis, the models for the primary outcome variables (Part-O and QoLIBRI) will include the intervention group, all the covariates that define the subgroups, and interactions between each covariate and the intervention group. Test of interactions will reveal if there are subgroups based on a certain covariate (or factor) that respond differently to the RDP or RTP intervention. It is possible that for some covariates, we will not have enough individuals to give information on the outcomes variation in a certain subgroup and that we will not be able to assess the effect for that covariate, while for other covariates, the sample size in each subgroup will be enough to provide information for the data analysis. These numbers cannot be determined a priori. For example, facility discharges are expected to occur in approximately 198 participants (22%) of our sample which will allow adequate sample size for comparison, and males are expected to make up approximately 612 participants and can be compared to females. We may have difficulty comparing race/ethnicity on more specific subgroups such as Asians (expected to be approximately 2% of our participants) and Hawaiian/Pacific Islander (expected to be <1%), but will likely have an adequate sample size to compare Hispanic (11%) to non-Hispanic and Black (17%), White (73%), and other (10%). In this situation, we may have to collapse the categories into a smaller number, such as White, non-Hispanic Black, Hispanic, and Other. Given multiple insurance options across the population as well as across the sites we may not have adequate power to detect differences between every provider, but will explore the effect of relevant subgroups such as private insurance vs. Medicaid vs. Medicare, for example.

We will explore the effects of the intervention on patient subgroups defined by factors known or hypothesized to have associations with poorer TBI outcome: facility vs. community discharge, race/ethnicity (White, non-Hispanic Black, Hispanic, Other), age (as continuous), male vs. female, lack of or lower degree of caregiver involvement (yes or no), severity of TBI (moderate vs. severe), presence of pre-injury psychosocial limitations (e.g., unemployment, substance abuse, categorized in yes or no) and medical or psychiatric comorbidity (yes or no), as well as study site, resource variability and insurance type (private insurance vs. Medicaid vs. Medicare). These factors will be entered in a single linear regression model in addition to the intervention group, using PART-O-17 as the response variable. Interactions between each factor and the intervention group will be entered in the model and test of interaction will be the test of heterogeneity. Before constructing the model, we will assess whether the explanatory variables (factors) are correlated to each other.

When two or more variables are deemed highly correlated, to avoid problems with collinearity, we will construct the model with the variable that provides the best model (from fit and diagnostic tests).

From previous research, we hypothesize that severity of TBI and presence of pre-injury psychosocial limitations will interact with the intervention group. With our expected sample size, we anticipate being able to address these questions. Some of the factors might not have a statistically significant effect, but have the effect in the expected direction. Effect sizes and confidence intervals will be calculated to express the potential effect of those factors. The results of these analyses will be valuable in designing future studies.

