#### *Inclusion Criteria-Patient Participants*

(1) Hospitalized with a moderate-to-severe TBI defined by TBIMS and this study as damage to brain tissue caused by an external mechanical force as evidenced by medically documented loss of consciousness or post-traumatic amnesia (PTA) due to brain trauma or by objective neurological findings that can be reasonably attributed to TBI on physical examination or mental status examination. Potential participants must meet at least one of the following criteria to be considered experiencing a moderate-to-severe TBI:

- (a) PTA>24 hours;
- (b) Trauma related intracranial neuroimaging abnormalities;
- (c) Loss of consciousness exceeding 30 minutes (unless due to sedation or intoxication); or
- (d) Glasgow Coma Scale in the emergency department of less than 13 (unless due to intubation, sedation, or intoxication).

(2) English speaking (we will track non-enrollment due to other language to determine common languages and have consumer dissemination materials translated for more broad use if time and resources permit.);

(3) at least 18 years old;

(4) will be discharged from inpatient rehabilitation to community (private residence, adult home, hotel, homeless) or facility (nursing home, subacute care i.e. skilled nursing facility);

- (5) current admission to inpatient rehabilitation considered their first comprehensive rehabilitation experience, or extension thereof for most recent TBI(e.g. admitted to inpatient rehabilitation, discharged to acute care, then returns to inpatient rehabilitation to complete their initial stay);
- (6) able to provide informed consent, or if unable to provide consent have family or legal guardian to provide informed consent for the patient.

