#### **Analysis of heterogeneity of treatment effects (HT-1, HT-3, HT-4)**

We will explore the differential effects of the intervention on patient subgroups defined by factors known or hypothesized to have associations with poorer TBI outcome: facility vs. community discharge, minority race/ ethnicity, older age, male gender, lack of or lower degree of caregiver

involvement, greater severity of TBI, presence of pre-injury psychosocial limitations (e.g., unemployment, substance abuse) and medical or psychiatric comorbidity, as well as study site, resource variability and insurance type. These factors will be entered in a single linear regression model in addition to the intervention group, using PART-O-17 as the response variable. Before constructing the model, we will assess whether the explanatory variables are correlated to each other. When two or more variables are deemed highly correlated, to avoid problems with collinearity, we will construct the model with the variable that provides the best model (from fit and diagnostic tests). From previous research, we hypothesize that severity of TBI and presence of pre-injury psychosocial limitations will interact with the intervention group, and those interactions will be included in the model. With our expected sample size we anticipate being able to address these questions.

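### Injury severity, one of two hypothesised effect modifiers, enters the interaction model as a moderate/severe split with no instrument or cut, although graded measures are collected

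*Combined protocol and SAP*

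**What the plan says.** Under Heterogeneity of Treatment Effects, the subgroup factors go into a single linear regression of PART-O-17, each with a product term with arm. Severity is listed as "severity of TBI (moderate vs. severe", and age in the same list as "age (as continuous". Two factors carry an actual hypothesis: "we hypothesize that severity of TBI and presence of pre-injury psychosocial limitations will interact with the intervention group". The section expects the sample size to suffice but gives no interaction power.

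The later section, Analysis of heterogeneity of treatment effects, lists "greater severity of TBI, presence of pre-injury psychosocial limitations" with no coding. It names only the severity and psychosocial product terms for inclusion.

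The patient inclusion criteria define one combined class: "Potential participants must meet at least one of the following criteria to be considered experiencing a moderate-to-severe TBI". The four routes are amnesia beyond 24 hours, "Trauma related intracranial neuroimaging abnormalities", loss of consciousness beyond 30 minutes, and "Glasgow Coma Scale in the emergency department of less than 13 (unless due to intubation, sedation, or intoxication". Nothing divides that class into moderate and severe.

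Patient Population says that Glasgow Coma Scale (GCS) scores are captured (mean 9.91) "in addition to multiple other severity indicators (imaging, duration of coma, PTA". Data Sources and Resources says that the same data elements, which include injury severity, are collected from participants outside the TBI Model Systems cohort.

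**The concern.** Two things look wrong. First, the binary is undefined. GCS, amnesia duration, coma duration and imaging could each supply it, and they would not sort patients the same way. A patient admitted on an abnormal scan with GCS 13–15 and brief amnesia could be placed differently by each.

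Second, even a well-defined split discards gradation within each half. The loss falls on one of the two interactions for which the trial has a prior hypothesis, and interaction tests are weak to begin with. A null result for severity would then be hard to read: it could mean no modification, or a blunt measure.

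An undefined severity variable also appears as an adjustment factor for Aim 2, and as a possible one for Aim 3, so one definition would serve all three analyses.

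**Working it through.** **Is there a figure to reproduce?** No. The documents give no power, precision or information figure for the severity interaction.

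**Inputs from the documents:** planned enrolment 900; 80% retention, so 0.80 × 900 = 720; two-sided 0.05; 1:1 allocation; mean GCS 9.91. The GCS spread, the share classed severe and the size of the interaction are not given, so they are assumed below.

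**Formula.** Arm is randomised and so independent of severity. If the arm difference changes linearly with severity, the information for the interaction that survives a split is the squared correlation between the binary and the graded measure. For a normal measure with share *p* classed severe, this is φ(z)² / [p(1 − p)], where z is the point that cuts off *p*. For a uniform measure it is 3p(1 − p).

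- Normal, 50:50: 0.3989² / 0.25 = 0.637, so 36% is lost.
- Normal, 70:30: 0.3477² / 0.21 = 0.576, so 42% is lost.

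For GCS itself, three assumed shapes on scores 3 to 15 were tilted to a mean of 9.91 and cut, again by assumption, at 8 or below.

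| Assumed severity measure | Share severe | Information lost |
|---|---|---|
| Normal | 50% | 36% |
| Normal | 40% | 38% |
| Normal | 30% | 42% |
| Normal | 20% | 51% |
| Normal | 10% | 66% |
| Uniform | 50% | 25% |
| Uniform | 30% | 37% |
| Uniform | 20% | 52% |
| GCS, near-flat | 36% | 27% |
| GCS, heavy at both ends | 39% | 13% |
| GCS, U-shaped | 40% | 13% |

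The loss is smallest when patients already cluster at the extremes, because a split then describes them fairly well. It is largest when the split is lopsided.

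**In patients.** For a normal measure, 1/0.637 = 1.57 and 1/0.576 = 1.74. For this test only, keeping the graded measure is worth 57% to 74% more patients. Equivalently, a 50:50 split makes 720 patients carry the information of 0.637 × 720 ≈ 458.

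**In power.** Assume a normal measure, outcome SD 1 and an interaction of 0.20 outcome SD per SD of severity (the documents state none). The standard error is 2/√N, which is 0.0667 at 900 and 0.0745 at 720. Power is Φ(0.20·√retained / SE − 1.96).

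| N | Graded | 50:50 split | 35% severe |
|---|---|---|---|
| 900 | 0.85 | 0.67 | 0.64 |
| 720 | 0.77 | 0.57 | 0.55 |

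Example at 720, graded: 0.20/0.0745 = 2.68, and Φ(2.68 − 1.96) = 0.77.

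**The case against.** The sponsor can fairly say that this is exploratory work meant to inform later studies, and that the factors were chosen for relevance to delivering the intervention in clinics, where two categories are easier to use. The later section mentions no split at all. The replication section places data definitions and coding instructions in the Manual of Procedures, which is not part of these documents, so a cut may exist there. Graded measures also have faults. Patients can be enrolled by proxy before emerging from amnesia, so its duration is censored. GCS is qualified by intubation, sedation and intoxication. All of this stands. It limits the weight of the point but does not defend the split, because nothing in the documents argues for two categories over a graded term.

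Several stronger readings are tempting and are not supported:

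- *Scan-positive patients with GCS 13–15 have no category.* This presumes a GCS-only cut that is never stated. Under the inclusion criteria they belong to the combined class and could be called moderate. Their placement is unspecified, not absent.
- *The loss is about 40%.* That needs a normal measure and a split of roughly 60:40 to 70:30. Neither is documented.
- *Unclassified patients drop out of every interaction test.* The missing-data text under Data Analysis Plan allows imputation and, for a missing covariate, removal of the covariate.
- *The orientation testing in Recruitment shows that graded amnesia data are stored.* That section says those scores are not entered as data. Availability rests on Patient Population and Data Sources and Resources.
- *The insurance levels leave the same gap.* The heterogeneity text introduces them as examples, so this is at most missing detail.

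**Conclusion.** The point holds as a matter of definition and efficiency. Severity is a hypothesised effect modifier, it is reduced to an undefined binary in one section and left uncoded in the other, and graded data exist. Under a linear modifying effect, the split costs about 36% to 42% of the interaction information for a normal measure at 50:50 to 70:30. Across other plausible distributions and splits the cost runs from about 13% to over 50%. Every scenario examined shows a loss, but the documents do not allow a narrower statement. If the modification were a step at the chosen cut and not a gradient, these losses would not apply.

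The documents do not show that the cut would be picked after seeing the data, only that they do not fix it. The primary comparison of arms is untouched, so this is a worthwhile improvement and not a flaw in the trial.

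**What to change.** In both heterogeneity sections, name one graded severity measure, continuous or ordinal, and use the same wording. Amnesia duration is a candidate, with a stated rule for patients who have not yet emerged; an ordinal coding with a top not-emerged class would avoid inventing a value. GCS could serve as a sensitivity analysis, with a coding rule for scores affected by intubation, sedation or intoxication. Test the measure's interaction with arm, and report the arm difference with its confidence interval at a few severity values fixed in advance. If two groups are kept for display, state the instrument and the cut, and say where each of the four eligibility routes falls. Apply the same definition wherever injury severity is an adjustment factor in Aims 2 and 3.

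The cost is plan wording, with no new data collection. Results are slightly harder to present than two subgroups, and the censored amnesia values need explicit handling.
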